1.2.1 Estimands

Primary estimand defined for main endpoints are summarized in below [Table 2](#). More details are provided in [Section 4](#).

Table 2 - Summary of primary estimand for main endpoints

Endpoint Category	Estimands			Population-level summary
	Endpoint ^a	Population	Intercurrent event(s) strategy and missing data handling	
Primary objective: To demonstrate the efficacy of dupilumab in adult and adolescent participants with primary acquired chronic inducible ColdU who remain symptomatic despite the use of an H1-antihistamine				
Primary endpoint	Proportion of participants with negative ice cube provocation test at Week 24	ITT	
The intercurrent events will be handled as follows:
 
Discontinuation of study intervention before Week 24 (but not taking highly influential prohibited medications and/or highly influential rescue medications ^b prior to Week 24): Off-study intervention data up to Week 24 will be included in the analysis (treatment policy strategy).Taking highly influential prohibited medications and/or highly influential rescue medications ^b prior to Week 24: Participants will be considered as having positive ice cube provocation tests at Week 24 (composite strategy). 
In addition, the missing data imputation rules are as follows:
 
Having missing data at Week 24: Participants will be considered as having positive ice cube provocation tests at Week 24.	CMH test stratified by region (combined countries) and background H1-antihistamine regular/daily use (Yes/No). The comparison of the proportions of treatment response between dupilumab and placebo will be derived, and the corresponding odd ratios and the 95% CI will be reported.

Endpoint Category	Estimands			Population-level summary
	Endpoint ^a	Population	Intercurrent event(s) strategy and missing data handling	
Secondary objective: To demonstrate the efficacy of dupilumab on primary acquired chronic inducible ColdU local signs and symptoms				
Secondary endpoint	
Change from baseline in local wheal intensity at the provocation site at Week 24 using the wheal intensity Likert scale ranging from 0 to 5 (clinician evaluation)
 
Change from baseline in the proportion of cold urticaria sign and symptom free days at Week 24 on cold exposure days as measured by ColdUAS
	ITT	
The intercurrent events will be handled as follows:
 
 Discontinuation of study intervention before Week 24 (but not taking highly influential prohibited medications and/or highly influential rescue medications ^b prior to Week 24): Off-study intervention data up to Week 24 will be included in the analysis (treatment policy strategy) Taking highly influential prohibited medications and/or highly influential rescue medications ^b prior to Week 24: data will be set to missing values after the medication usage, and WOCF approach (worst post-baseline observation for the participant will be carried forward) will be used to impute missing endpoint value (for participants whose post-baseline values are all missing, the participant's baseline value will be used to impute the missing endpoint value) (composite strategy) 
In addition, the missing data imputation rules are as follows:
 
 For participants who discontinue study intervention due to lack of efficacy, all data collected after discontinuation will be used in the analysis, and a WOCF approach will be used to impute missing Week 24 value if needed. For participants who discontinue study intervention not due to lack of efficacy, a multiple imputation approach will be used to impute missing Week 24 value, and this multiple imputation will use all participants excluding participants who have taken the highly influential prohibited medications and/or highly influential rescue medications ^b on or before Week 24 and excluding patients who discontinue due to lack of efficacy on or before Week 24. 	
ANCOVA model with treatment group, baseline value, region (combined countries), and background H1-antihistamine regular/daily use (Yes/No) as covariates will be used. Statistical inference obtained from all imputed data by ANCOVA model will be combined using Rubin's rule. Descriptive statistics including number of participants, mean, standard error, and least squares (LS) mean changes (and standard error) score will be provided. In addition, difference of the dupilumab group against placebo in LS means and the corresponding 95% CI will be provided along with the p-values.


^a Additional secondary objectives/endpoints are not included in this table but would be handled with a similar strategy as the endpoint type (i.e., Continuous, proportion) at other weeks

^b Highly influential prohibited medications and/or highly influential rescue medications are listed in [Table 4](#).

2 SAMPLE SIZE DETERMINATION

Sample size is calculated based on the following assumptions:

1. The placebo group has █ participants with negative ice cube provocation test at Week 24 and the dupilumab group has █ participants with negative ice cube provocation test at Week 24.
2. There is a drop-out rate of 10% in both groups.
3. The statistical test is a Z test that is based on the difference of the 2 proportions with unpooled variance estimate and 2-sided 1% significance level.
4. Participants are equally randomized to the dupilumab group and the placebo group.

With these assumptions, 39 participants per group (78 participants in total) will provide 90% power to detect the difference of █ response rate in the dupilumab group and █ response rate in the placebo group. The sample size calculations were performed using nQuery+nTerim 4.0.

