9.2 SAMPLE SIZE DETERMINATION

To adequately power the study for the comparison of the primary endpoint of the proportion of participants with negative ice cube provocation test at Week 24 between the 2 groups, the sample size was calculated based on the following assumptions:

1. The placebo group has █ of participants with negative ice cube provocation test at Week 24 and the dupilumab group has █ of participants with negative ice cube provocation test at Week 24.
2. There is a drop-out rate of 10% in both groups.
3. The statistical test is a Z test that is based on the difference of the 2 proportions with unpooled variance estimate and 2-sided 1% significance level.
4. Participants are equally randomized to the dupilumab group and the placebo group.

With these assumptions, 39 participants per group (78 participants in total) will provide 90% power to detect the difference of █ response rate in the dupilumab group and █ response rate in the placebo group. The sample size calculations were performed using nQuery+nTerim 4.0.

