4.3.2 Main analytical approach

The primary analysis population for the efficacy endpoints will be the ITT population. The statistical hypotheses for comparing dupilumab against placebo on the primary endpoint of proportion of participants with negative ice cube provocation test at Week 24:

- Null hypothesis H0: No treatment difference between dupilumab and placebo.
- Alternative hypothesis H1: There is a treatment difference between dupilumab and placebo.

For efficacy analysis, [Table 4](#) presents the highly influential prohibited medications and highly influential rescue medications which will be considered as intercurrent events if the last column indicates as “Yes” and confirmed through blinded medical review and therefore will be handled in the estimands for endpoints defined in [Table 2](#). Blinded medical review of participants who received the medications listed in [Table 4](#) will be implemented before database lock to ensure the medication use was due to treatment failure instead of an unrelated condition.

Table 4 - Highly influential prohibited medications and/or highly influential rescue medications impact on efficacy

Medication	Comment	Highly influential (Yes/No) ^a / Selection criteria
Systemic immunosuppressants (immunosuppressive/immunomodulating drugs) e.g., systemic corticosteroids (oral or parenteral [intravenous, intramuscular, SC]), cyclosporine, mycophenolate-mofetil, interferon gamma, Janus kinase inhibitors, azathioprine, methotrexate, hydroxychloroquine, dapsone, sulfasalazine, colchicine, etc.	IMP to be discontinued	Yes (Standardized drug groupings (SDGs) Other immunosuppressants, tumour necrosis factor (TNF) alpha inhibitors, Calcineurin inhibitors, Interleukin inhibitors, Selective immunosuppressants – all Narrow)
Any cell-depleting agents including but not limited to rituximab		Yes (CDG10236 Cell depletion agents)
Other monoclonal antibodies (which are biological response modifiers) including anti-IgE therapy (omalizumab).		Yes (SDG Monoclonal antibodies Narrow)
IVIG		Yes (CDG00488 Intravenous immunoglobulin therapy - See Section 5.5)
Plasmapheresis		Yes (CMQ00079 based on the following PTs: Plasmapheresis, Apheresis)
Other investigational drugs.		No, except ones with mechanism of action that may impact efficacy
Topical corticosteroids.	No IMP discontinuation	No
Topical calcineurin inhibitors.		No
Topical and oral antihistamines (other than those allowed as background therapy).		No

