Routine doses of doxepin (daily or every other day during 5 or more consecutive days).		No
LTRAs and H2 receptor antagonists, unless stable and taken for diseases other than chronic inducible ColdU.		Yes for LTRAs; No for H2 receptor antagonists (SDG Leukotriene receptor antagonists for obstructive airway diseases Narrow)
Antifibrinolytic tranexamic acid and epsilon-aminocaproic acid		No
Phototherapy, including tanning beds.		No
Additional H1-AH up to 4-fold (2-fold in Japan)	No IMP discontinuation	No
Corticosteroids		Yes (SDG Corticosteroids Narrow excluding where Route is Topical, Nasal, Respiratory (Inhalation) or Ophthalmic)

a When yes, if confirmed through blinded medical review that the medication use was due to treatment failure instead of an unrelated condition, the estimand for the intercurrent event handling strategy will be as follows: composite for continuous and responder endpoints. Otherwise, a treatment policy strategy will be applied.

The intercurrent event handling strategy for the primary estimand is the treatment policy/composite approach.

The primary efficacy endpoint will be analyzed using the Cochran-Mantel-Haenszel test stratified by region (combined countries) and background H1-antihistamine regular/daily use (Yes/No). The comparison of the proportions of participants with negative ice cube provocation test at Week 24 between dupilumab and placebo will be derived, and the corresponding odd ratios and the 95% confidence interval (CI) will be reported. Participants who receive highly influential prohibited medications and/or highly influential rescue medications (see [Table 4](#)) will be considered as having positive ice cube provocation tests for time points after the medication usage. For other participants, all available data including those collected during the off-treatment period will be used to determine the positive/negative ice cube provocation test outcome. Participants with missing ice cube provocation test data at Week 24 will be considered as having positive ice cube provocation tests.

The following is a sample code for the primary analysis.

```
proc freq data=dataice;  
  tables region*background*trtgrp*response/relrisk cmh;  
  weight Count;  
run;
```

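### Does the stated 90% power fail to apply because the trial is sized on an unpooled Z test but analysed with a stratified CMH test that counts missing tests as positive?

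*SAP*

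**What the plan says.** SAP section 2, Protocol section 9.2 and the Protocol synopsis carry the same calculation. The test is a "Z test that is based on the difference of the 2 proportions with unpooled variance estimate and 2-sided 1% significance level", allocation is 1:1, and "There is a drop-out rate of 10% in both groups". On that basis "39 participants per group (78 participants in total) will provide 90% power". Both response rates are blacked out. Protocol section 9.2 introduces the calculation with the words "To adequately power the study for the comparison of the primary endpoint".

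SAP section 4.3.2 then defines the primary analysis. "The primary analysis population for the efficacy endpoints will be the ITT population". "The primary efficacy endpoint will be analyzed using the Cochran-Mantel-Haenszel test stratified by region (combined countries") and by background H1-antihistamine use. "Participants with missing ice cube provocation test data at Week 24 will be considered as having positive ice cube provocation tests". For participants who have not taken a highly influential medication, "all available data including those collected during the off-treatment period will be used", so stopping treatment does not by itself make the Week 24 result missing.

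The two-sided 1% level agrees between SAP section 2 and SAP section 4.6.

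**The concern.** The sizing test and the deciding test differ in two ways.

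First, the unpooled Z test and the CMH test use different variances, and at this sample size they do not have the same power.

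Second, the usual allowance for drop-out, dividing the evaluable number by 0.9, assumes that those who drop out leave the denominator. Here they stay in it as non-responders. If a fraction *m* of Week 24 tests is missing in each arm, both rates are multiplied by (1 − *m*) and the difference shrinks by the same factor. Dividing by 0.9 does not make up for that.

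If the redacted rates describe participants with a Week 24 result, the deciding analysis would have less than the 90% on which 78 participants are justified. A non-significant primary result at the 1% level would then be read against an overstated power. Type I error would not be affected.

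**Working it through.** **Inputs from the documents.** Two-sided alpha 0.01, so z = 2.576; 90% power, so z = 1.282; 39 per arm; 10% drop-out; 1:1 allocation.

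**Assumed, because the rates are redacted.** Placebo rates of 2, 5, 10, 20 and 40%. For each, the dupilumab rate is solved so that the stated Z test has exactly 90% power at 35 evaluable per arm.

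**1. The plan's own figure.** The 90% cannot be reproduced directly without the rates. The sample size is coherent: 35 / 0.9 = 38.9, rounded up to 39. That the 10% was applied in this way is an inference. The formula is

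power = Φ( (p2 − p1) / √{[p1(1 − p1) + p2(1 − p2)] / n} − 2.576 ).

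Example with placebo 10%, dupilumab 48%, n = 35: the variance sum is 0.0900 + 0.2496 = 0.3396, the standard error is √(0.3396/35) = 0.0985, 0.38/0.0985 = 3.858, and Φ(3.858 − 2.576) = Φ(1.282) = 90%.

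**2. Same formula with the rule applied.** With 10% missing, the rates become 9% and 43.2% at n = 39. The variance sum is 0.0819 + 0.2454 = 0.3273, the standard error is 0.0916, 0.342/0.0916 = 3.733, and Φ(3.733 − 2.576) = Φ(1.157) = 87.6%.

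**3. The Mantel-Haenszel statistic itself.** This is exact enumeration in a single stratum, (Σ(x − E))²/V with the hypergeometric variance V, rejecting above 6.635 (2.576²). Power in %:

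| Placebo rate | Solved dupilumab rate | 35 per arm, nobody recoded | 39 per arm, none missing | 39, 5% missing = positive | 39, 10% missing = positive |
|---|---|---|---|---|---|
| 2% | 34% | 90.0 | 93.8 | 91.9 | 89.4 |
| 5% | 40% | 88.1 | 91.6 | 89.1 | 86.1 |
| 10% | 48% | 86.1 | 90.8 | 88.1 | 84.8 |
| 20% | 61% | 85.4 | 88.6 | 85.2 | 81.4 |
| 40% | 81% | 85.2 | 88.7 | 82.8 | 76.4 |

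The column for 39 with none missing is the case in which the redacted rates already include the rule.

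**4. Splitting the shortfall.** The third column differs from 90% only because the test changes from the unpooled approximation to Mantel-Haenszel: 0, 1.9, 3.9, 4.6 and 4.8 points. Going from the third to the last column, that is, recoding 10% as positive at 39 per arm instead of losing them, costs a further 0.6, 2.0, 1.3, 4.0 and 8.8 points. At placebo rates of 10 and 20% the change of test accounts for at least half of the loss; at 5% the two parts are about equal; at 40% the rule dominates.

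**5. Stratification.** A simulation of the six-stratum CMH test (three regions by H1-antihistamine use; 40,000 replicates; randomization stratified as planned; assumed country shares, block size 4 and 50% regular use) gives 88.9, 86.0, 83.5, 80.7 and 76.1% with 10% missing. The gap from the last column is 0.5, 0.1, 1.3, 0.7 and 0.3 points, so stratifying costs about one point or less.

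**The case for a change.** The strongest argument for a change is that a separate drop-out allowance makes sense only if the assumed rates are for participants with a Week 24 result, and that is the reading under which power is lost. If the rates already include the rule, the 10% has no job to do. Either way SAP section 2 leaves something unexplained, the sponsor holds the rates, and one calculation would settle it.

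Part of this stands. The documents do not say how the 10% was applied, whether the rates include the rule, or what power the CMH test has. The drop-out line does lean towards the less favourable reading.

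It does not go further than that. SAP section 2 states the rates as participants with a negative test at Week 24, and section 4.3.2 scores that endpoint with missing counted as positive, so the benign reading is open on the text.

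Nor is drop-out the same as a missing test. Protocol section 7.1.1 asks those who stop treatment early to attend the remaining visits. Off-treatment results count, and SAP Table 10 maps Days 127 to 210 to Week 24. Against this, Protocol section 7.1.1 bars further tests after a systemic reaction to the ice cube. The missing share is therefore unknown and could fall on either side of 10%.

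The largest losses need high placebo rates. Inclusion criterion I 03 requires a positive test at both screening and randomization, which makes such rates less likely, though this too is an inference.

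**Conclusion.** No change follows. The 90% is a planning figure for a named test under listed assumptions, and it is coherent with 39 per arm. Sizing on a simple Z test and analysing with a stratified CMH test is a common simplification, and stratification costs about a point or less.

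A shortfall cannot be shown from the documents. It depends on redacted rates, on whether they include the missing-equals-positive rule, and on an unstated share of missing tests. If the rates include the rule, single-stratum power at 39 per arm is about 89 to 94% over assumed placebo rates of 2 to 40%. If they do not and 10% of tests are missing, it is about 85 to 89% at placebo rates of 2 to 10%, and 81% and 76% at 20 and 40%. With 5% missing it is 88 to 92% at 2 to 10%. The change of test contributes up to about 5 points of the loss independently of the rule.

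What remains is missing detail in the account of the sample size. Supplying it would leave the sample size, alpha, primary test and missing-data rule as they are. Randomization began on 04 January 2021 and this SAP follows the amendment of 27 September 2022, so a restated power figure would come too late to inform the design. Once the trial reports, the confidence interval for the treatment effect will show the precision achieved.

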3 ANALYSIS POPULATIONS

The following populations for analyses are defined:

Table 3 - Populations for analyses

Population	Description
Screened	All participants who sign the ICF
Randomized	All participants from the screened population who have been allocated to a randomized intervention by IRT regardless of whether the treatment kit was used or not. Participants treated without being randomized will not be considered randomized and will not be included in any efficacy population.
Intent-to-treat (ITT)	All randomized participants analyzed according to the intervention group allocated by randomization.
Safety	All participants randomly assigned to study intervention and who take at least 1 dose of study intervention. Participants will be analyzed according to the intervention they actually received. Randomized participants for whom it is unclear whether they took the study medication will be included in the safety population as randomized. For participants who accidentally receive a different intervention from that which was planned, the actual intervention allocation for as-treated analysis will be the dupilumab group. The pharmacodynamic (PD) analyses will be performed on the safety population.
Pharmacokinetic (PK)	The PK population includes all participants in the safety population with at least one non-missing result for functional dupilumab concentration in serum after first dose of the study intervention. Participants will be analyzed according to the intervention actually received.
Anti-drug antibody (ADA)	ADA population includes all participants in the safety population who have at least one non-missing ADA result after first dose of the study intervention. Participants will be analyzed according to the intervention actually received.

Abbreviations: ITT = intent-to-treat, ADA = antidirug antibody; ICF = Informed consent form, IRT = Interactive response technology; PD = Pharmacodynamic, PK = Pharmacokinetic

Participants exposed to study intervention before or without being randomized will not be considered randomized and will not be included in any analysis population. The safety experience of these participants will be reported separately.

Randomized participants for whom it is unclear whether they took the study intervention will be considered as exposed and will be included in the safety population as randomized.

For any participant randomized more than once, only the data associated with the first randomization will be used in any analysis population. The safety experience associated with any later randomization will be reported separately.

For participants receiving more than one study intervention (placebo and dupilumab) during the study, the intervention group for as-treated analysis will be the dupilumab group.

If >10% participants are impacted by the COVID-19 pandemic, additional summaries by COVID-19 subgroups will be provided. Participants impacted by the COVID-19 pandemic are

defined as randomized participants with any critical or major deviation related to COVID-19 or who permanently discontinued study intervention or study due to COVID-19.

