Participants will be randomized in a 1:1 ratio to dupilumab or placebo. The randomization will be first stratified by age (adults versus adolescents) with at least 4 adolescents. Then in adult's randomization will be stratified further by country and background H1-antihistamine regular/daily use (Yes/No). Randomization will not be stratified further in adolescents.

Number of participants using H1-antihistamine as needed prior to study entry should be at least █.

- **Analysis population**

The primary analysis population for the efficacy endpoints will be the randomized intent-to-treat population which includes all participants who have been allocated to a randomized treatment regardless of whether the treatment kit was used or not. The efficacy analyses will be conducted according to the treatment to which they were randomized.

The analysis population for safety endpoints is defined as all randomized participants exposed to study medication, regardless of the amount of treatment administered. The safety analyses will be conducted according to the treatment participants actually received.

- **Primary analysis**

The primary efficacy endpoint is the proportion of participants with negative ice cube provocation test at Week 24. The statistical hypothesis for comparing dupilumab against placebo on the primary endpoint is:

- Null hypothesis H0: No treatment difference between dupilumab and placebo.
- Alternative hypothesis H1: There is a treatment difference between dupilumab and placebo.

The primary efficacy endpoint will be analyzed using the Cochran-Mantel-Haenszel test stratified by region and background H1-antihistamine regular/daily use (Yes/No). The comparison of the proportions of participants with negative ice cube provocation test at Week 24 between dupilumab and placebo will be derived, and the corresponding odd ratios and the 95% confidence interval (CI) will be reported. Participants who receive highly influential prohibited medications and/or highly influential rescue medications (details of selection will be specified in the statistical analysis plan [SAP]) will be considered as having positive ice cube provocation tests for time points after the

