9.3 POPULATIONS FOR ANALYSES

The analysis populations are defined in [Table 6](#).

Table 6 - Analyses population

Population	Description
Screened	All participants who sign the ICF
Randomized	The randomized population includes all participants with a treatment kit number allocated and recorded in the IRT database, and regardless of whether the treatment kit was used or not. Participants treated without being randomized will not be considered randomized and will not be included in any efficacy population.
Intent-to-treat (ITT)	All randomized participants analyzed according to the treatment group allocated by randomization.
Efficacy	The ITT population
Safety	All participants randomly assigned to IMP and who take at least 1 dose of study IMP. Participants will be analyzed according to the intervention they actually received. Randomized participants for whom it is unclear whether they took the study IMP will be included in the safety population as randomized. For participants who accidentally receive different treatment from the planned, the actual intervention allocation for as-treated analysis will be the dupilumab group. The PD analyses will be performed on the safety population.
Pharmacokinetic (PK)	The PK population includes all participants in the safety population with at least 1 non-missing result for functional dupilumab concentration in serum after first dose of the IMP. Participants will be analyzed according to the intervention actually received.
Antidrug antibody (ADA)	ADA population includes all participants in the safety population who have at least 1 non-missing ADA result after first dose of the IMP. Participants will be analyzed according to the intervention actually received.

Abbreviations: ADA = antidrug antibody; ICF = Informed consent form, IMP = investigational medicinal product; IRT = Interactive response technology; ITT = intent-to-treat; PD = Pharmacodynamic; PK = Pharmacokinetic.

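### The accidental-treatment sentence in the safety population puts a participant randomised to dupilumab who took only placebo in the dupilumab group, against the as-treated rule

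*SAP*

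**What the plan says.** The Safety row of SAP Section 3, Table 3, gives the general rule: "Participants will be analyzed according to the intervention they actually received". The protocol synopsis states the same principle: "The safety analyses will be conducted according to the treatment participants actually received".

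The same SAP row then adds an exception. Its trigger is "For participants who accidentally receive a different intervention from that which was planned", and its result is "the actual intervention allocation for as-treated analysis will be the dupilumab group". Protocol Section 9.3, Table 6, carries the exception in nearly the same words: "For participants who accidentally receive different treatment from the planned, the actual intervention allocation for as-treated analysis will be the dupilumab group". Neither version states the direction of the error or requires exposure to dupilumab. The Safety row in both documents also governs the pharmacodynamic analyses.

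The text below SAP Table 3 has a narrower rule. It opens "For participants receiving more than one study intervention (placebo and dupilumab) during the study" and assigns those participants to dupilumab. It does not say that it limits or replaces the sentence in the table. The protocol has no counterpart to it.

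The PK and ADA rows, in both documents, have their own allocation rule and no exception. In the SAP it reads "Participants will be analyzed according to the intervention actually received".

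**The concern.** An as-treated safety analysis should attribute adverse events and laboratory values to the product the person was exposed to. The accidental-treatment sentence gives a fixed answer, dupilumab, whatever was taken. Where a participant randomised to dupilumab took nothing but placebo, that answer contradicts the sentence that opens the allocation rule in the same table row.

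The safety tables and the total IgE summaries are at stake. Total IgE is summarised in the safety population (SAP Section 4.8.3). A second problem is consistency. The same person could be counted as dupilumab for safety and IgE but as placebo for ADA and, if a concentration result exists, for PK. If programmers instead derive one actual-treatment variable that carries the exception, PK handling changes too. SAP Section 4.8.1 sets post-baseline values below the quantification limit to half that limit for drug-treated participants, but to zero for placebo. The text does not say which approach to take.

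**Working it through.** There is no plan figure to reproduce. The check sets the rules against each possible misallocation, treating the two interventions as dupilumab and placebo.

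**Step 1. Enumerate the cases.**

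| Randomised to | Product taken | General as-treated rule | Accidental-treatment sentence | SAP rule for both products |
|---|---|---|---|---|
| Placebo | Dupilumab only | Dupilumab | Dupilumab | Not triggered |
| Placebo | Both | No single answer | Dupilumab | Dupilumab |
| Dupilumab | Both | No single answer | Dupilumab | Dupilumab |
| Dupilumab | Placebo only | **Placebo** | **Dupilumab** | Not triggered |

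The sentence is harmless or helpful in the first three rows. The fourth is a direct contradiction, and nothing else in either document settles it.

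**Step 2. Weight of one such participant.** Inputs: 39 per group (SAP Section 2), assuming all are treated and exactly one falls in the fourth row.

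- Share of the dupilumab denominator: 1/39 = 2.6%.
- Denominators under the accidental-treatment sentence: 39 dupilumab, 39 placebo.
- Denominators as actually received: 39 − 1 = 38 dupilumab, 39 + 1 = 40 placebo.

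**Step 3. Direction.** Take a preferred term with two events in the group randomised to dupilumab and, by assumption, none among those randomised to placebo.

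- *The misallocated participant has one of the two events.* Dupilumab rate under the sentence: 2/39 = 5.1%. As received: 1/38 = 2.6%, with placebo 1/40 = 2.5%. The sentence raises the dupilumab rate.
- *The misallocated participant has no event.* Under the sentence: 2/39 = 5.1%. As received: 2/38 = 5.3%. The sentence lowers the dupilumab rate slightly.

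In the first example the term passes the 5% cut in SAP Section 4.7.2 under one rule and falls below it in both groups under the other. That cut decides which preferred terms get risk differences and hazard ratios. These are constructed illustrations, not expected effects.

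**The case against.** The strongest defence is that the sentence is a loose form of a sensible convention: any dupilumab exposure counts as dupilumab. The SAP text below the table ends in the same words and spells out that both products were received, which suggests a shared intent. On that reading no one meant to classify a placebo-only participant as dupilumab. The trigger is also narrow. Study drug is given every two weeks from Day 1 to Week 22, from kits allocated centrally. One correct dupilumab dose makes the participant a recipient of both products, and the rules then agree. The conflict needs every dose taken to be placebo, through repeated error or a wrong kit followed by early discontinuation. SAP Section 4.7 plans no safety testing, and ITT efficacy follows randomisation.

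All of this stands as to rarity and consequence. It does not remove the contradiction, because the intended condition is not written in either table.

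A reader might infer more than the documents support:

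- *That the sentence misplaces everyone given the wrong product.* It gives the right group in three of the four cases.
- *That placebo-only data would enter the dupilumab PK and ADA summaries.* The PK and ADA rows follow treatment received and lack the exception. The problem there is possible inconsistency between populations.
- *That active-arm event rates would be diluted.* Direction depends on whether the participant had the event, as Step 3 shows.

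**Conclusion.** Wrong as written, at low severity. In one configuration (randomised to dupilumab, only placebo taken) SAP Table 3 and protocol Table 6 each give two incompatible group assignments, and the SAP rule for recipients of both products does not resolve them. Each such participant carries about 2.6% of the planned arm, in either direction, in the safety and total IgE summaries, and may be grouped differently in ADA or PK. The 2.6% assumes 39 treated participants in the arm. It is the weight of one case. The documents give no rate for such errors, so no expected impact can be stated. The primary and other ITT efficacy analyses are unaffected.

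**What to change.** In the Safety row of both SAP Table 3 and protocol Table 6, limit the accidental-treatment sentence to participants who received at least one dose of dupilumab. Add that participants who received only placebo are analysed in the placebo group, whatever their randomised arm. This leaves the other three cases unchanged and aligns the Safety row with the PK and ADA rows.

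Do not simply delete the sentence. In the SAP, the general rule and the text below the table would still classify every case. In the protocol, deletion would remove the only rule for participants who received both products. Placebo-only participants should also be named, because the SAP text below the table does not mention them and their group otherwise follows only from the general sentence.

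The cost is one clause and one added statement in each document, with no new data. The protocol change is a protocol edit and should be handled as one. Both changes should be made before database lock and unblinding, so that no group assignment is decided after results are known.
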